9.3.7. Treatment and Follow-Up of Adverse Events (AEs)

Adverse events, especially those for which the relationship to rilzabrutinib or placebo is “related”, should be followed-up until they have returned to baseline status or stabilized.

If after follow-up, return to baseline status or stabilization cannot be established an explanation should be recorded on the eCRF.

9.3.8. Laboratory and Electrocardiogram (ECG) Abnormalities

Laboratory test results will appear on electronically produced laboratory reports or be recorded on the laboratory results pages of the eCRF if applicable.

Any treatment-emergent abnormal laboratory or ECG result which is clinically significant, ie, meeting one or more of the following conditions, should be recorded as a single diagnosis on the AE page in the eCRF:

- Accompanied by clinical symptoms
- Leading to a change in rilzabrutinib or placebo (eg, dose interruption or permanent discontinuation)
- Requiring a change in concomitant therapy (eg, addition of, interruption of, discontinuation of, or any other change in a concomitant medication, therapy, or treatment)

Note: Any laboratory or ECG result abnormality fulfilling the criteria for an SAE should be reported as such, in addition to being recorded as an AE in the eCRF.

9.3.8.1. Follow-Up of Abnormal Laboratory Test Values

In the event of unexplained clinically significant abnormal laboratory test values, the tests should be repeated as soon as possible, no later than 72 hours after reporting of the results and should be followed-up until they have returned to the normal range and/or an adequate explanation of the abnormality is found. If a clear explanation is established, it should be recorded on the eCRF.

9.3.9. Adverse events (AEs), Serious Adverse Events (SAEs) and Other Safety Reporting

The definitions of AEs and SAEs can be found in [Appendix 12](#). The definition of adverse event of special interest (AESI) is provided in Section [9.3.9.6](#).

The Investigator and any qualified designees are responsible for detecting, documenting, and recording events reported by the participant (or, when appropriate, by a caregiver, surrogate, or the participant's legally authorized representative) that meet the definition of an AE or SAE and remain responsible for following up AEs, particularly those that are serious, considered related to the study intervention or study procedures, or that caused the participant to discontinue the study intervention or study (see Section [7.5](#)).

The method of recording, evaluating, and assessing causality of AEs and SAEs and the procedures for completing and transmitting SAE reports are provided in [Appendix 12](#).

9.3.9.1. Time period and frequency for collecting AE and SAE information

All AEs (serious or nonserious) will be collected from the signing of the ICF until the follow-up visit at the time points specified in the SoA ([Table 1](#), [Table 2](#), and [Table 3](#)).

All AEs will be collected from the signing of the ICF at the time points specified in the SoA ([Table 1](#), [Table 2](#), and [Table 3](#)).

All SAEs and AESIs will be recorded and reported to the Sponsor or designee immediately and under no circumstance should this exceed 24 hours, as indicated in [Appendix 12](#). The Investigator will submit any updated SAE data to the Sponsor within 24 hours of it being available.

Investigators are not obligated to actively seek information on AEs or SAEs after conclusion of the study participation. However, if the Investigator learns of any SAE, including a death, at any time after a participant has been discharged from the study, and he/she considers the event to be reasonably related to the study intervention or study participation, the Investigator must promptly notify the Sponsor.

9.3.9.2. Method of detecting AEs and SAEs

Care will be taken not to introduce bias when detecting AEs and/or SAEs. Open-ended and non-leading verbal questioning of the participant is the preferred method to inquire about AE occurrences.

9.3.9.3. Follow-up of AEs and SAEs

After the initial AE/AESI/SAE report, the Investigator is required to proactively follow each participant at subsequent visits/contacts. At the pre-specified study end-date, all SAEs, and other AEs, will be followed until resolution, stabilization, the event is otherwise explained, or the participant is lost to follow-up (as defined in Section 7.5.3). Further information on follow-up procedures is provided in [Appendix 12](#).

9.3.9.4. Regulatory reporting requirements for SAEs

- Prompt notification by the Investigator to the Sponsor of an SAE is essential so that legal obligations and ethical responsibilities towards the safety of participants and the safety of a study intervention under clinical investigation are met.
- The Sponsor has a legal responsibility to notify both the local regulatory authority and other regulatory agencies about the safety of a study intervention under clinical investigation. The Sponsor will comply with country-specific regulatory requirements relating to safety reporting to the regulatory authority, IRB/IEC, and Investigators.
- Serious adverse events that are considered expected will be specified in the reference safety information in the Investigator's Brochure.
- Investigator safety reports must be prepared for SUSARs according to local regulatory requirements and Sponsor policy and forwarded to Investigators as necessary.
- An Investigator who receives an Investigator safety report describing an SAE, SUSAR or any other specific safety information (eg, summary or listing of SAEs) from the Sponsor will review and then file it along with the Investigator's Brochure and will notify the IRB/IEC, if appropriate according to local requirements. It is the responsibility of the Sponsor to assess whether an event meets the criteria for a SUSAR, and therefore, is expedited to regulatory authorities.
- For the European Union, safety reporting to the agency is described in [Appendix 10.7](#).

9.3.9.5. Pregnancy

- Details of all pregnancies will be collected after the start of study intervention and until 28 days after the last dose of study intervention.
- If a pregnancy is reported after the first dose of the IMP, the Investigator will record pregnancy information on the appropriate form and submit it to the Sponsor within 24 hours of learning of the pregnancy.
- While pregnancy itself is not considered to be an AE or SAE, any pregnancy complication or elective termination of a pregnancy for medical reasons will be reported as an AE or SAE.
- Abnormal pregnancy outcomes (eg, spontaneous abortion, fetal death, stillbirth, congenital anomalies, ectopic pregnancy) are considered SAEs and will be reported as such.
- The participant/pregnant female partner will be followed to determine the outcome of the pregnancy. The Investigator will collect follow-up information on the participant/pregnant female partner and the neonate, and the information will be forwarded to the Sponsor.
- Any post-study pregnancy-related SAE considered reasonably related to the study intervention by the Investigator will be reported to the Sponsor as described in [Appendix 12](#). While the Investigator is not obligated to actively seek this information in former study participants/pregnant female partners, he or she may learn of an SAE through spontaneous reporting.
- Any female participant who becomes pregnant while participating in the study must discontinue study intervention or be withdrawn from the study.

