4.1.4. End of Study visit (Four Weeks Post Last Dose of Study Drug)

The following assessments will be performed four weeks post last dose of study drug in the double blind, open label period, or LTE:

- Complete ITP-PAQ or ITP-KIT, EQ-5D-5L and PGIS-Fatigue/PGIS/PGIC patient questionnaire
- Record concomitant medications
- Record AEs

- Record weight (kg)
- Conduct full physical examination; See [Appendix 10.6](#) for Italy-specific requirements
- Complete IBLS
- Capture vital signs (body temperature, respiratory rate, blood pressure, and pulse rate)
- Collect 12-lead single ECG
- Collect urine sample for urinalysis
- Conduct urine pregnancy test (women of childbearing potential)
- Collect clinical laboratory blood samples:
 - Hematology (hemoglobin, hematocrit, RBCs, platelets, mean platelet volume, WBCs with differentials [neutrophils, eosinophils, basophils, lymphocytes, and monocytes])
 - Serum chemistry (AST, ALT, bilirubin, ALP, albumin, creatinine, urea, total protein, sodium, chloride, calcium, phosphate, potassium, and glucose [random])
 - Coagulation (PT/INR, thrombin time, aPTT, fibrinogen level)
- Collect exploratory laboratory blood samples (see [Appendix 10](#) for country-specific requirements):
 - T/B/NK counts
 - TPO levels
 - Hemolysis panel
 - Immunoglobulin levels
 - (Optional) vaccine-specific IgG response
- For country-specific requirements please refer to [Appendix 10](#).

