5. ELIGIBILITY CRITERIA

5.1. Inclusion Criteria

Participants may be included in the study if ALL of the following criteria are met:

1. Participants will be male and female with primary ITP with duration of >6 months in pediatric participants aged 12 to <18 years (pediatric participants aged 10 to <12 years will be enrolled in the EU [EEA countries] only; refer to [Appendix 10.2](#), [Appendix 10.3](#), and [Appendix 10.7](#) for country-specific requirements) and duration of >3 months in adults aged ≥ 18 years
2. Participants who had a response (achievement of platelet count $\geq 50,000/\mu\text{L}$) to IVIg/anti-D or CSs that was not sustained and who have documented intolerance, insufficient response, or any contraindication to any appropriate courses of standard of care ITP therapy
3. An average of 2 platelet counts at least 5 days apart of $<30,000/\mu\text{L}$ during the screening period and no single platelet count $>35,000/\mu\text{L}$, within 14 days prior to the first dose of study drug
 - Pediatric participants must additionally be determined to need treatment for ITP as per clinical assessment by the Investigator (see [Appendix 10.7](#) for EU [EEA countries] specific criteria)
4. Adequate hematologic, hepatic, and renal function (absolute neutrophil count $\geq 1.5 \times 10^9/\text{L}$, AST/ALT $\leq 1.5 \times$ upper limit of normal (ULN), albumin ≥ 3 g/dL, total bilirubin $\leq 1.5 \times$ ULN [unless the participant has documented Gilbert syndrome], estimated glomerular filtration rate (GFR) >50 [Cockcroft and Gault method for adult and Bedside Schwartz Equation for Pediatric participants])
5. Hemoglobin >9 g/dL within 1 week prior to Study Day 1
6. All contraceptive use by men and women should be consistent with local regulations regarding the methods of contraception for those participating in clinical studies.

A) Male participants

Male participants are eligible to participate if they agree to the following during the intervention period and for at least 13 weeks after the last administration of study intervention:

- Refrain from donating or cryopreserving sperm
- Plus, either:
- Be abstinent from heterosexual intercourse as their preferred and usual lifestyle (abstinent on a long term and persistent basis) and agree to remain abstinent
- OR
- Must agree to use contraception/barrier as detailed below

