 - A male condom; the participant should also be advised of the benefit for a female partner to use a highly effective method of contraception (as described in [Appendix 13](#) Contraceptive and barrier guidance) of the protocol as a

condom may break or leak when having sexual intercourse with a woman of childbearing potential (WOCBP) who is not currently pregnant

B) Female participants

A female participant is eligible to participate if she is not pregnant or breastfeeding, and one of the following conditions applies:

- Is a woman of nonchildbearing potential (WONCBP) as defined in [Appendix 13](#) of the protocol.

OR

- Is a WOCBP and agrees to use a contraceptive method that is highly effective (with a failure rate of <1% per year), as described in [Appendix 13](#) of the protocol, during the study intervention period (to be effective before starting the intervention) and for at least 4 weeks after the last administration of study intervention AND agrees not to donate or cryopreserve eggs (ova, oocytes) for the purpose of reproduction during this period.
- A WOCBP must have a negative highly sensitive pregnancy test (serum) as required by local regulations) within 3 days before the first administration of study intervention
 - If a urine test cannot be confirmed as negative (eg, an ambiguous result), a serum pregnancy test is required. In such cases, the participant must be excluded from participation if the serum pregnancy result is positive.

7. Participants must be able to provide written informed consent or informed assent with corresponding informed consent obtained from the participants' guardian and agree to the SoA.

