9.3.9.6. Adverse events of special interest

An AESI is an AE (serious or nonserious) of scientific and medical concern specific to the Sponsor's product or program, for which ongoing monitoring and immediate notification (within 24 hours) by the Investigator to the Sponsor is required. Such events may require further investigation in order to characterize and understand them. Adverse events of special interest may be added, modified, or removed during a study by protocol amendment; they include:

- Pregnancy of a female participant entered in a study and received at least one dose of the IMP as well as pregnancy occurring in a female partner of a male participant entered in a study with IMP;
 - Pregnancy occurring in a female participant entered in the clinical trial or in a female partner of a male participant entered in the clinical trial will be qualified as an SAE only if it fulfills one of the seriousness criteria (see [Appendix 12](#)).
 - In the event of pregnancy in a female participant, IMP must be discontinued.
 - Follow-up of the pregnancy in a female participant or in a female partner of a male participant is mandatory until the outcome has been determined (See [Appendix 13](#)).
- Symptomatic overdose (serious or nonserious) with IMP

- Increase in ALT $>3 \times$ ULN (See [Appendix 15](#) for follow-up instructions). If such laboratory values have been determined, follow-up within 72 hours of the same value and total bilirubin levels is required and if value is repeated (eg, ALT $>3 \times$ ULN), such value shall be reported as well together with the repeated total bilirubin values and any other laboratory values to determine the cause of the initially determined ALT increase.
- Any Grade 4 or 5 infection where the participant is hospitalized ≥ 24 hours and/or requires emergency care and/or requires intravenous antibiotics.
- Any occurrence of uveitis (including Vogt-Koyanagi-Harada disease [VKHD])

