Appendix 13.2 Contraception guidance

Participants should be given advice about donation and cryopreservation of germ cells prior to the start of the study intervention, in line with the fact that study intervention may affect ova up to 4 weeks and sperm up to 13 weeks (see inclusion criteria).

If locally required, acceptable contraceptive methods are limited to those which inhibit ovulation as the primary mode of action.

CONTRACEPTIVES ^a ALLOWED DURING THE STUDY INCLUDE:

Highly effective methods^b that have low user dependency Failure rate of <1% per year when used consistently and correctly.
 
 • Implantable progestogen-only hormone contraception associated with inhibition of ovulation^c • Intrauterine device (IUD) • Intrauterine hormone-releasing system (IUS)^c • Bilateral tubal occlusion • Azoospermic partner (vasectomized or due to a medical cause) 
Azoospermia is a highly effective contraceptive method provided that the partner is the sole sexual partner of the woman of childbearing potential and the absence of sperm has been confirmed. If not, an additional highly effective method of contraception should be used.
 
Note: documentation of azoospermia for a male participant can come from the site personnel's review of the participant's medical records, medical examination, or medical history interview.

Highly effective methods^b that are user dependent Failure rate of <1% per year when used consistently and correctly.
 
Combined (estrogen- and progestogen-containing) hormonal contraception associated with inhibition of ovulation^c
 
 • oral • intravaginal • transdermal • injectable 
Progestogen-only hormone contraception associated with inhibition of ovulation^c
 
 • Oral • injectable 
Sexual abstinence
 
Sexual abstinence is considered a highly effective method only if defined as refraining from heterosexual intercourse during the entire period of risk associated with the study intervention. The reliability of sexual abstinence needs to be evaluated in relation to the duration of the study and the preferred and usual lifestyle of the participant.

- a* Contraceptive use by men or women should be consistent with local regulations regarding the use of contraceptive methods for those participating in clinical studies.

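### Pregnancy collection stops 28 days after the last dose, leaving 63 of the 91 post-dose days of the protocol's own sperm window without active collection for partners of male participants

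*Protocol*

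**What the plan says.** Protocol Section 9.3.9.5 (Pregnancy) fixes a single collection period for every pregnancy: "Details of all pregnancies will be collected after the start of study intervention and until 28 days after the last dose of study intervention". It makes no distinction between a pregnant participant and a pregnant partner.

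Elsewhere the protocol does distinguish the sexes. Appendix 13.2 states that "study intervention may affect ova up to 4 weeks and sperm up to 13 weeks". Inclusion criterion 6 in Section 5.1 follows the same split. Men must observe the contraception and sperm-donation rules "for at least 13 weeks after the last administration of study intervention", and women must use contraception "for at least 4 weeks after the last administration of study intervention AND agrees not to donate or cryopreserve eggs".

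Partner pregnancies are in scope. Section 9.3.9.6 lists as an AESI "pregnancy occurring in a female partner of a male participant entered in a study with IMP" and makes follow-up to outcome mandatory. Section 9.3.9.5 asks for follow-up of the pregnant partner and the neonate, and Section 12.2 provides for the partner's consent. SAP Table 8 selects pregnancy among the AESIs to be analysed.

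The last scheduled contact is the End of Study visit in Section 4.1.4: "The following assessments will be performed four weeks post last dose of study drug in the double blind, open label period, or LTE".

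**The concern.** The protocol names two periods of possible effect after the last dose, one for ova and one for sperm, but collects pregnancies over only the shorter one. A partner conception in weeks 5 to 13 falls in the period the protocol treats as relevant for men, yet lies beyond both the collection limit and the last scheduled visit. From then on, nobody is asked to look for it.

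At stake is how completely one named AESI is ascertained. If late partner pregnancies reach the database only when a participant happens to mention them, the number of paternal-exposure pregnancies and the record of their outcomes may fall short. Contraceptive failures in those nine weeks are the events most easily missed.

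**Working it through.** The plan gives no figure for this coverage, so there is none to reproduce. The check is day arithmetic on the protocol's own periods.

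**Inputs**
- End of collection, all pregnancies: 28 days after the last dose (Section 9.3.9.5).
- Possible effect on ova: 4 weeks (Appendix 13.2; the same period for women in inclusion criterion 6).
- Possible effect on sperm: 13 weeks (Appendix 13.2; the same period for men in inclusion criterion 6).
- Last scheduled contact: 4 weeks after the last dose (Section 4.1.4).
- Treatment length for illustration: 24 weeks (blinded period completed) and 24 + 28 = 52 weeks (blinded plus open label).

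**Post-dose window**
- Female participants: 4 × 7 = 28 days; gap = 28 − 28 = 0 days.
- Partners of male participants: 13 × 7 = 91 days; gap = 91 − 28 = 63 days = 9 weeks.
- Share of the post-dose window without active collection: 63 / 91 = 69%.

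**Whole window, treatment included**
- 24 weeks of treatment: 9 / (24 + 13) = 9 / 37 = 24%.
- 52 weeks of treatment: 9 / (52 + 13) = 9 / 65 = 14%.
- The share falls further with time in the long-term extension.

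**Routes still open after day 28**

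| Route | End date | Active or passive |
|---|---|---|
| Section 9.3.9.5, first bullet (collection period) | 28 days after last dose | Closed |
| Section 9.3.9.5, second bullet (a pregnancy reported after first dose goes to the sponsor within 24 hours of the investigator learning of it) | None stated | Passive |
| Section 9.3.9.6 (partner pregnancy as an AESI) | None stated | Passive once visits have ended |
| Section 9.3.9.5, post-study pregnancy-related SAE judged related | None stated | Passive; the investigator need not seek it |

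No section sets a longer active collection period for partners. The first and second bullets of Section 9.3.9.5 also sit awkwardly together, since one has a limit and the other has none. A site could reasonably read them either way.

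**The case against.** A reader might infer that a partner pregnancy after day 28 cannot be recorded at all, or only as a related SAE. The documents do not support that. The second bullet of Section 9.3.9.5 requires a reported pregnancy to be recorded and sent on, with no end date and no relatedness condition, and the AESI text has no end date either. What is missing is active collection.

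A reader might also take the 69% as the share of all partner exposure. It is not, because time on treatment is covered in full; the whole-window figures are much lower.

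Nor can it be said that counts will be understated. The documents give neither the number of male participants nor a partner-pregnancy rate. Contraception or abstinence is already required for the full 13 weeks, so mainly contraceptive failures are at issue. Section 2.3 reports no genotoxicity and no toxicity in fertility and early embryo-fetal studies, and Appendix 13.2 words the effect as a possibility. Expected numbers may be small.

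Finally, with 2:1 allocation about one third of participants receive placebo in the blinded period. Men on placebo who stop without entering open label have no rilzabrutinib exposure to follow. This narrows who is truly exposed, but assignment is blinded, so a collection rule cannot readily separate them in advance.

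These points limit the size of the concern. They do not remove the mismatch: the contraception requirement lowers the number of events but does not detect the failures, and passive routes depend on chance.

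**Conclusion.** The mismatch stands. Sections 9.3.9.5, 9.3.9.6, Appendix 13.2 and inclusion criterion 6 need to be reconciled. For female partners of male participants, 63 of 91 post-dose days (69%) have no active collection. That is about 24% of the whole window with 24 weeks of treatment and about 14% with 52 weeks. There is no gap for female participants.

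The consequence is that partner-pregnancy counts may be understated; by how much cannot be estimated from the documents. The conclusion takes the protocol's 13-week sperm statement as it stands and offers no view on whether that period is clinically right.

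This is a worthwhile and inexpensive improvement to safety data collection. It does not touch the primary or key secondary analyses, the sample size or the power.

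**What to change.** In Section 9.3.9.5, set the period by who was exposed, using the protocol's own figures:

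- Female participants: keep 28 days after the last dose.
- Female partners of male participants: collect pregnancies conceived up to 13 weeks after the last dose, and accept later reports of such pregnancies. Defining the period by conception matters because a conception near Week 13 may not yet be recognised at that point.
- Leave the AESI text in Section 9.3.9.6 without a cut-off and refer it to this window. Adding a 13-week limit there would narrow text that now has none.
- At the End of Study visit, tell male participants to report any such partner pregnancy.
- Optionally, add one remote contact at or shortly after Week 13. It should not be the only safeguard, since a single call could miss late conceptions.

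The cost is amendment and consent wording, and possibly one contact about nine weeks after the End of Study visit (13 − 4 = 9). If the contact is added, check the stated participation of up to 60 weeks (Section 4.1) and the completion definition based on the last participant's last visit (Section 4.1.5). The SAP should also say how pregnancies reported after the end of study are presented, because its LTE post-treatment period (Section 3.1) ends there.
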